3 OBJECTIVES AND ENDPOINTS

3.1 Objectives, Hypotheses, and Estimands

Objectives

Primary

The primary study objective, related to Study Period 1, is to assess the efficacy and safety of upadacitinib, initiated at 15 mg once daily (QD) and dose adjusted based on clinical response, compared with dupilumab as per its label.

An additional objective, related to Study Period 2, is to assess the efficacy and safety of upadacitinib, initiated at 15 mg QD and dose adjusted based on clinical response, in subjects with inadequate response to dupilumab.

The primary efficacy objective is based on the achievement of a composite endpoint of at least a 90% reduction in EASI from baseline (EASI 90) and a Worst Pruritus Numerical Rating Scale of 0 or 1 (WP-NRS 0/1) at Week 16 with the treatment of upadacitinib compared with dupilumab per its label in the Intent-to-Treat (ITT) Population, which consists of all randomized subjects (Section 7.2).

Secondary

The secondary efficacy objectives are based on ranked secondary endpoints as defined in Section 3.3 with the treatment of upadacitinib compared with dupilumab in the ITT Population.

Hypotheses and Estimands for the Primary and Ranked Secondary Endpoints

The hypothesis corresponding to the primary efficacy endpoint (Section 3.2) is:

- The proportion of subjects achieving both EASI 90 and WP-NRS 0/1 at Week 16 in those treated with upadacitinib is greater than those treated with dupilumab.

The estimand corresponding to the primary endpoint is defined using the composite variable strategy, as follows:

- Difference in the proportion of subjects achieving both EASI 90 and WP-NRS 0/1 at Week 16 without the use of rescue medication, regardless of treatment discontinuation, between upadacitinib and dupilumab in the adolescent and adult subjects with moderate to severe AD who have inadequate response to systemic therapy.

The hypotheses and estimands corresponding to the ranked secondary endpoints are summarized below.

- Hypotheses: the proportion of subjects achieving each ranked endpoint in those treated with upadacitinib is greater than those treated with dupilumab

- Estimands: Difference in proportion of subjects achieving each of ranked secondary endpoints without the use of rescue medication, regardless of treatment discontinuation, between upadacitinib and dupilumab in the adolescent and adult subjects with moderate to severe AD who have inadequate response to systemic therapy.

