5.6 Follow-Up After Subject Discontinuation of Study Drug or from Study

Discontinuation of Study Drug

Subjects who prematurely discontinue study drug treatment will be discontinued from study participation entirely.

Following discontinuation of study drug, the subject should be treated in accordance with the investigator's best clinical judgment based on available approved treatment options.

If a subject prematurely discontinues study drug, the procedures outlined for the Premature Discontinuation visit (PD Visit) should be completed as soon as possible, preferably within 2 weeks, and preferably prior to initiation of another therapy. In addition, an End of Treatment Follow-up Visit after the last dose of study drug is required to ensure all treatment-emergent AEs/SAEs have been resolved. The 30-day or 12-week follow-up phone call (for subjects on upadacitinib or dupilumab, respectively) following the last dose of study drug will not be required for any subject who initiates commercially available upadacitinib or dupilumab upon the study Completion Visit or Premature Discontinuation visit. The End of Treatment Follow-up Visit is defined as:

- For subjects on upadacitinib, a 30-day follow-up visit (or phone call if a visit is not possible) after the last study drug dose will be completed to determine the status of any new or ongoing AEs/SAEs and concomitant medications.
- For subjects receiving dupilumab, a 12-week follow-up visit (or phone call if a visit is not possible) after the last study drug injection will be completed to determine the status of any new or ongoing AEs/SAEs and concomitant medications.

For subjects who prematurely discontinued study participation, this visit may be a telephone call if a site visit is not possible.

Premature Discontinuation of Study (Withdrawal of Informed Consent)

If a subject prematurely discontinues study participation (withdrawal of informed consent), the procedures outlined for the Premature Discontinuation visit (PD Visit) should be completed as soon as possible, preferably within 2 weeks, and preferably prior to initiation of another therapy. In addition, if subject is willing, a 30-day or 12 week follow-up phone call or visit after the last dose of study drug (for upadacitinib and dupilumab, respectively) may be completed to ensure all treatment-emergent AEs/SAEs have been resolved.

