## **7.2 Medical History and Prior and Concomitant Medications**

Medical history data will be coded using the Medical Dictionary for Regulatory Activities (MedDRA). The actual version of the MedDRA coding dictionary will be noted in the statistical tables and clinical study report. The number and percentage of subjects in each medical history category (by MedDRA system organ class (SOC) and preferred term) will be summarized overall and by treatment group for the safety Populations. The SOC will be presented in alphabetical order, and the preferred terms will be presented in alphabetical order within each SOC. Subjects reporting more than one condition/diagnosis will be counted only once in each row (SOC or preferred term).

A prior medication is defined as any medication taken prior to the date of the first dose of study drug. Prior medications will be summarized in the Safety Populations.

- A concomitant medication in Period 1 is defined as any medication that started prior to the date of the first dose of study drug in Period 1 and continued to be taken after the first dose of study drug in Period 1; or any medications taken after the first dose of study drug and within 1 day of the last dose of study drug for the subjects on upadacitinib in Period 1, and within 14 days of the last dose of study drug for the subjects on dupilumab in Period 1, respectively.
- A concomitant medication in Period 2 is defined as any medication that started prior to the date of the first dose of study drug in Period 2 and continued to be taken after the first dose of study drug in Period 2 or any medications, other than study drug, taken after the first dose of study drug and within 1 day of the last dose of study drug in Period 2.

Concomitant medications will be summarized by periods in each Safety Population. Prior medications will be summarized in the Safety Populations. The number and percentage of subjects taking medications will be summarized by generic drug name based on the World Health Organization (WHO) Drug Dictionary for both prior and concomitant medications.

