## **8.0 Handling of Potential Intercurrent Events for the Primary and Secondary Endpoints**

All efficacy endpoints (defined in Section 3.1, Section 3.2, and Section 3.3) will be analyzed based on the ITT 1 Population in Period 1 and ITT 2 Population in Period 2.

The following combined composite variable strategy and treatment policy strategy intercurrent events (ICEs) handling method will be used as the primary approach to handle intercurrent events in this study for all efficacy endpoints:

Subjects will be considered as non-responders after the initiation of rescue medication (composite variable strategy); and the value for the variable of interest is used regardless of treatment discontinuation (treatment policy strategy)

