## **Appendix F. Rescue Definition**

The topical and systemic medications for AD therapy are coded to the following drug classes. Among these AD medications, the potential AD rescue medications are determined through a medical review process.

1. Plain Topical Corticosteroids
2. High Potency Topical Corticosteroids
3. Medium Potency Topical Corticosteroids
4. Low Potency Topical Corticosteroids
5. Topical Calcineurin Inhibitor Therapy
6. Other Topical therapy (not including moisturizers/emollients)

Concomitant medications that are categorized as "potential AD rescue" per medical review AND in categories 1 - 6 above are considered as rescue medications in Period 1 and Period 2.

The medical review process is documented in the Rescue Medication Medical Review Process - Upadacitinib AD.

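### Rescue depends on a concomitant-medication window that closes 1 day after the last upadacitinib dose but 14 days after the last dupilumab dose, so a topical started after stopping can escape the estimand, and does so differently by arm

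*Protocol*

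**What the plan says.** Four rules combine.

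- **What rescue is.** SAP Appendix F starts from concomitant medications. Those that medical review flags as potential rescue "AND in categories 1 - 6 above are considered as rescue medications in Period 1 and Period 2". All six categories are topical.
- **When a medication is concomitant.** SAP 7.2 includes drugs continued from before first dose and drugs taken after it. For Period 1 it bounds the latter by the last dose: "within 1 day of the last dose of study drug for the subjects on upadacitinib in Period 1", but "within 14 days of the last dose of study drug for the subjects on dupilumab in Period 1".
- **What rescue does.** Under SAP 8.0 and 9.2 a subject is a non-responder once rescue has begun. If study drug is stopped without rescue, the observed value is used. The estimand in Protocol 3.1 asks for response "without the use of rescue medication, regardless of treatment discontinuation".
- **When the last assessment happens.** Protocol 5.6 takes subjects who stop study drug out of the study and lets them be treated as the investigator judges best. It says the discontinuation visit "should be completed as soon as possible, preferably within 2 weeks, and preferably prior to initiation of another therapy". The activity schedule (Protocol Appendix D) collects EASI and WP-NRS at that visit.

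**The concern.** Appendix F takes a term that SAP 7.2 defines for medication summaries and uses it to define an intercurrent event. Because that term is bounded by the last dose, a flagged topical started after the bound but before an assessment used in the analysis falls outside rescue. The value obtained on that topical can then count as a response that the estimand would score as failure. The bound also differs by arm, so the same topical at the same interval after the last dose can be scored in opposite ways.

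At stake are the primary endpoint and the ranked secondary endpoints, including those at Weeks 2 and 4 when a discontinuation visit falls near them. The NRI and MI sensitivity analyses use the same rescue definition, so neither would reveal the problem.

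**Working it through.** **1. The rule by day.** Let d be the number of days from the last dose to the start of a flagged topical. Applying the SAP 7.2 windows through Appendix F gives:

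| d | Upadacitinib | Dupilumab |
|---|---|---|
| 0–1 | rescue | rescue |
| 2–14 | not rescue | rescue |
| 15 or more | not rescue | not rescue |

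The arms differ on 14 − 1 = 13 days. From day 15 the topical escapes in both.

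**2. Early stopper.** Last dose Day 15, topical from Day 20 (d = 5), discontinuation visit Day 27. The window ends on Day 16 for upadacitinib and Day 29 for dupilumab. The topical is rescue on dupilumab only. If Day 27 lies in the Week 4 window (scheduled Day 29), the upadacitinib value is used as observed for ranked endpoints 4 and 6. The WP-NRS rolling average for Day 27 covers Days 21–27, all on the topical.

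**3. Cases that reverse the direction.** Dupilumab every other week from Day 1 puts Week 12 on Day 85 and Week 14 on Day 99. SAP 6.0 makes Week 14 the last planned dose.

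- Week 14 injection missed: the window ends on Day 85 + 14 = Day 99. A topical from Day 100 is not rescue, and the Week 16 value (Day 113) is used.
- Week 16 attended late: the window ends on Day 99 + 14 = Day 113. If the visit may be 7 days late (an assumption, because the visit-window row in Protocol Appendix D is hard to read), a topical started on Days 114–120 before the visit is not rescue.

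In both cases an upadacitinib subject still dosing who starts the same topical is a non-responder.

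**4. The plan's own power figure.** SAP 2.4 has 440 per arm, 12% versus 29%, two-sided 0.05. With a mean rate of 0.205, z = [0.17 × √440 − 1.96 × √(2 × 0.205 × 0.795)] / √(0.12 × 0.88 + 0.29 × 0.71) = (3.566 − 1.119) / 0.558 = 4.38. Power is 0.99999, in line with the stated figure of more than 90%. About 117 per arm would give 90%.

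**5. Size of the part that favours upadacitinib.** One subject is 1/440 = 0.23 points. The excess is (share stopping early) × (share with the discontinuation visit in the Week 16 window) × (share starting a topical on days 2–14 before it) × (response rate). The documents give none of the first three, and no response rate for subjects who stop, so all inputs are assumptions:

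| Case | Product | Points | Subjects of 440 |
|---|---|---|---|
| Low | 0.05 × 0.10 × 0.10 × 0.12 | 0.006 | 0.03 |
| Middle | 0.10 × 0.25 × 0.30 × 0.29 | 0.22 | 1.0 |
| High | 0.15 × 0.50 × 0.50 × 0.29 | 1.1 | 4.8 |
| High, all respond | 0.15 × 0.50 × 0.50 × 1 | 3.75 | 16.5 |

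Even the last row leaves power at 0.999. At the planned rates about 40 upadacitinib responders would have to be lost before power fell below 90%, and 55 (128 down to 73, against 53 on dupilumab) before the result lost significance.

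**6. What cannot be sized.** The SAP refers to visit windows (9.2) and analysis window conventions (9.7) but does not state them. The documents also give no rate for missed Week 14 injections or late Week 16 visits, so the reverse part has no estimate.

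**The case against.** **The link is inferred.** Appendix F does not cite SAP 7.2, whose windows serve summaries in the Safety Populations, while efficacy uses the ITT populations. Protocol 5.4 records any medication received during the study. SAP 9.2 drops assessments after the start of rescue with no last-dose limit. The medical review is described in a separate document. This stands in part: if the programming does not apply the 7.2 windows, there is no gap. But the SAP offers no other definition of the term, and 9.2 acts only once a drug has been classed as rescue.

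**The windows mirror dosing intervals.** They do, and SAP 6.0 computes treatment duration in the same way. That is sensible for a summary table. It gives no reason to score an estimand event by dosing interval once values after stopping are used.

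**A topical after stopping is subsequent therapy under treatment policy.** Then it should not count on dupilumab either. Either reading needs one rule for both arms.

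**Most discontinuation visits miss the Week 16 window.** True. Week 16 is then normally missing and scored as non-response in both arms, which is the main reason the effect is small.

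**A stronger reading is tempting but not supported.** A reader might infer that the rule always favours upadacitinib, from an example with the last dose on Day 100 in both arms and a topical on Day 103. That is not identical conduct. A dupilumab subject last dosed about Day 100 has had every planned injection and is still within a dosing interval; the upadacitinib subject has stopped daily treatment. The cases in step 3 of the working also run the other way.

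**Conclusion.** The inconsistency is real on the literal text. Rescue is bounded by the last dose, the bound differs by arm, and the estimand contains neither feature. Among early stoppers, topicals started on days 2–14 after the last dose are failures on dupilumab and ignored on upadacitinib. Among dupilumab subjects who miss the Week 14 injection or attend Week 16 late, the gap can favour dupilumab. The net direction is unknown, and the documents do not support a claim of one-directional bias.

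The effect is probably well under 1 point. The assumed range is 0.006 to 1.1 points, and its upper end takes the highest figure for every share and gives subjects who stopped the whole arm's planned 29% response rate. Power and the primary conclusion are not at risk. The case for acting is that the definition should match the estimand, and that the correction is cheap. The decisive texts are SAP Appendix F and 7.2; Protocol 5.6 contains no error and shows only that the situation can arise.

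**What to change.** Add a short paragraph to SAP Appendix F stating that, for efficacy:

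- rescue is any category 1–6 medication flagged by medical review and used after the first dose of study drug, including one continued from before that dose;
- it applies to every assessment made after its first use following the first dose and, for WP-NRS, to every rolling average that includes days after that use;
- the date of the last study-drug dose plays no part, and the rule is identical in both arms;
- an assessment made before rescue on the same day is kept;
- the SAP 7.2 windows are used only for medication summaries.

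A simpler rule based on topicals started after first dose and on or before the assessment date would not do. It would drop topicals continued from before first dose, and it would fail subjects assessed before same-day rescue, which is the order that Protocol 5.4 asks for.

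The cost is one paragraph and a check that the medical review covers drugs started after the last dose. Concomitant therapy is already recorded at the discontinuation visit (Protocol Appendix D). Protocol 5.4 asks for start dates rather than times, so same-day order rests on its instruction to assess before rescue. No new data, visit or clinical rule is needed.

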Important Medical Event Requiring Medical or Surgical Intervention to Prevent Serious Outcome	An important medical event that may not be immediately life-threatening or result in death or hospitalization, but based on medical judgment may jeopardize the subject and may require medical or surgical intervention to prevent any of the outcomes listed above (i.e., death of subject, life threatening, hospitalization, prolongation of hospitalization, congenital anomaly, or persistent or significant disability/incapacity). Additionally, any elective or spontaneous abortion or stillbirth is considered an important medical event along with any suspected transmission of an infectious agent via a medicinal product if no other serious criterion is applicable. Examples of such events include allergic bronchospasm requiring intensive treatment in an emergency room or at home, blood dyscrasias or convulsions that do not result in inpatient hospitalization, or the development of drug dependency or drug abuse.

All adverse events reported from the time of study drug administration until 30 days or 5 half-lives, whichever is longer, after discontinuation of study drug administration will be collected, whether solicited or spontaneously reported by the subject. In addition, study procedure-related serious and nonserious adverse events will be collected from the time the subject signs the study-specific informed consent. If a subject prematurely discontinues study participation and begins commercially available upadacitinib drug (Rinvoq), all adverse events reported by healthcare professionals or the patient, will be captured as postmarketing reports. The 30-Day follow-up phone call following the last dose of upadacitinib study drug during the study will not occur for subjects who begin commercially available upadacitinib drug. Similarly, if a subject prematurely discontinues study participation and begins commercially available dupilumab drug (Dupixent), all adverse events reported by the healthcare professionals or the patient, will be captured as postmarketing reports. The 84-day (12 week) follow-up phone call following the last dose of dupilumab study drug during the study will not occur for subjects who begin commercially available dupilumab drug.

The following definitions will be used for Serious Adverse Reactions (SAR) and Suspected Unexpected Serious Adverse Reaction (SUSAR):

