7.5 Statistical Analyses for Safety

The safety analyses will be carried out using the Safety Population and will be based on treatments the subjects actually received. Safety will be assessed by AEs, physical examination, laboratory assessments, and vital signs. Note that missing safety data will not be imputed.

Adverse events will be coded using the Medical Dictionary for Regulatory Activities (MedDRA). Treatment-emergent adverse events (TEAEs) are defined as those that began or worsened in severity after the first dose of study drug and no more than 5 half-lives of the drug after the last dose of study drug. Specifically, 30 days will be used for upadacitinib, and 84 days (12 weeks) will be used for dupilumab. The number and percentage of subjects experiencing TEAEs will be tabulated using system organ class and preferred term, overall and by severity and by relationship to the study drug as assessed by the investigator by the Period using the Safety_1 population and Safety_2 population, respectively. Summaries (including percentages and events per 100 patient years) of TEAEs, AESIs, SAEs, deaths, and AEs leading to discontinuation will be provided in both Periods.

For laboratory tests and vital signs, mean change from baseline and percentage of subject with evaluations meeting pre-defined Potentially Clinically Important criteria will be summarized in both Periods. For selected lab parameters, a listing of all subjects with any laboratory value above Grade 3 of Common Toxicity Criteria will be provided. Additional details for the safety analysis will be provided in the SAP.

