## 2.2 Study Design Overview

This is a global, Phase 3b/4, randomized, open-label, efficacy assessor-blinded, multi-center study that will evaluate upadacitinib compared with dupilumab, as monotherapy, in adolescents and adult subjects ( $\geq 12$  and  $< 64$  years of age weighing at least 40 kg) with moderate to severe AD who have inadequate response to systemic therapy. Eligible subjects must have a documented history of inadequate response to at least one systemic treatment for AD prior to the Baseline Visit or for whom other systemic treatments are otherwise medically inadvisable.

The study will consist of a 35-day Screening Period; Period 1, a 16-week randomized, open-label, efficacy assessor blinded treatment period for all subjects, and a 30-day or 12-week follow-up visit for subjects on upadacitinib or dupilumab respectively, who will not enter the Period 2; Period 2, a 16-week open-label, efficacy assessor blinded extension period for those subjects with a  $< \text{EASI } 75$  response at Week 16 (total duration 32 weeks) and a 30-day follow-up visit. The 30-day or 12-week follow-up visit or phone call (for subjects on upadacitinib or dupilumab, respectively) following the last dose of study drug will not be required for any subject who initiates commercially available upadacitinib or dupilumab upon the Study Completion visit or Premature Discontinuation visit.

Sites will have the option to conduct the unscheduled visits/30-day or 12-week follow-up visit virtually during the course of the study as needed:

The study is comprised of two periods:

**Period 1:** A 16-week open-label, efficacy assessor blinded treatment period designed to evaluate the efficacy and safety of upadacitinib, initiated at 15 mg QD and dose adjusted based on clinical response starting after 4 weeks of treatment, compared with dupilumab as per its label. Subjects who meet eligibility criteria will be randomized in a 1:1 ratio to receive either upadacitinib 15 mg QD or dupilumab as per its label.

**Period 2:** An extension period to evaluate the efficacy and safety of upadacitinib, initiated at 15 mg QD and dose adjusted based on clinical response in subjects with inadequate

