### 10.2.1 Treatment-Emergent Adverse Events

Treatment-emergent adverse events (TEAEs) are defined as follows:

- TEAEs in Period 1 are defined as any adverse events that begin or worsen in severity after initiation of upadacitinib/dupilumab through the minimum (30 days following the last dose of upadacitinib in Period 1 or through 84 days following the last dose of dupilumab in Period 1, the start day of Period 2 – 1).
- TEAEs in Period 2 are defined as any adverse events that begin or worsen in severity after initiation of upadacitinib in Period 2 through 30 days following the last dose of upadacitinib in Period 2.
- TEAEs during the administration of upadacitinib are defined as any adverse events that begin or worsen in severity after initiation of upadacitinib through 30 days following the last dose of upadacitinib.

If a missing or an incomplete onset date is collected for an adverse event, the event will be assumed to be treatment-emergent unless there is other evidence that confirms that the event is not treatment-emergent (e.g., the event end date is prior to the study drug start date). Events where the onset date is the same as the study treatment start date are assumed to be treatment-emergent. All treatment-emergent AEs will be summarized overall, as well as by primary MedDRA SOC and Preferred Term. The SOCs will be presented in alphabetical order, and the PTs will be presented in alphabetical order within each SOC.

The number and percentage of subjects experiencing TEAEs and the number of events per 100 patient-years of exposure will be summarized.

TEAEs per 100 patient-years of exposure are defined as the number of TEAEs divided by the total exposure in 100 patient-years. See the calculation method below:

$$100 * (\text{Number of TEAEs}) / (\text{Total Patient Years})$$

where total patient years is defined as the sum of the study drug duration (defined in Section 6.0) of all subjects normalized by 365.25 and rounded to 1 decimal place.

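### Follow-up is waived for subjects who start commercial upadacitinib or dupilumab, but the 30/84-day adverse event and laboratory windows do not stop when they start it

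*Protocol*

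**What the plan says.** **Waiver.** In Protocol 5.6, and likewise in the Synopsis (Investigational Plan), the 30-day or 12-week call "will not be required for any subject who initiates commercially available upadacitinib or dupilumab upon the study Completion Visit or Premature Discontinuation visit". SAP 2.2 widens this to a visit or phone call, which "following the last dose of study drug will not be required for any subject who initiates commercially available upadacitinib or dupilumab".

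**Narrower waiver.** Protocol 6.1 ties the waiver to continuing the same drug. For subjects who begin commercial dupilumab, "The 84-day (12 week) follow-up phone call following the last dose of dupilumab study drug during the study will not occur"; a parallel sentence covers upadacitinib. The same section says that events in subjects who discontinue prematurely and begin the commercial drug "will be captured as postmarketing reports". It gives no such route for subjects who complete.

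**Collection rule.** Protocol 6.1 also says that adverse events "until 30 days or 5 half-lives, whichever is longer, after discontinuation of study drug administration will be collected".

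**Analysis windows.** Protocol 7.5 fixes the TEAE window: "Specifically, 30 days will be used for upadacitinib, and 84 days (12 weeks) will be used for dupilumab". SAP 10.2.1 counts Period 1 events to 30 days after the last upadacitinib dose or "through 84 days following the last dose of dupilumab in Period 1", cut at the day before Period 2 starts if that is earlier. SAP 10.3 includes laboratory values to the same 30 or 84 days, and SAP 10.2.2 and 10.2.4 split deaths at those limits. None of these rules mentions the start of commercial drug.

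**The concern.** The follow-up contact is the only one scheduled after the last on-treatment visit (Appendix D). When it is waived, the analysis window stays open but nothing is scheduled inside it. Two things follow.

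- In a table of the percentage of subjects with at least one TEAE, a waived subject stays in the denominator as event-free over time that nobody observed, unless an event reaches the site spontaneously.
- Under the either-drug wording, a dupilumab completer can start commercial upadacitinib at Week 16 with the dupilumab window still open. If an event is then reported to the trial, SAP 10.2.1 counts it as a Period 1 dupilumab TEAE. For subjects who make the same change inside the trial, the SAP closes the Period 1 window the day before Period 2. It applies no such rule to commercial starters.

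Subjects at or above EASI 75 leave the study at Week 16 in both arms (Protocol 4.1), so the group that could be waived may be large. Safety is part of the primary objective, and Protocol 5.10 provides no independent monitoring committee, so the rules that decide which events are counted should be explicit.

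**Working it through.** **Inputs.** Week 16 visit: Day 113 (Appendix D). Last planned dupilumab dose: Week 14 (SAP 6.0), so Day 1 + 14 × 7 = Day 99. Last upadacitinib dose: taken as Day 113; Day 112 would change 30 days to 29. Post-dose windows: 84 and 30 days (Protocol 7.5). Commercial uptake by arm: not given, so any share used here is an assumption.

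**The plan's own figure.** 12 weeks × 7 = 84 days, as stated.

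**Window per waived Week 16 completer**

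| | Dupilumab | Upadacitinib |
|---|---|---|
| Window ends | 99 + 84 = Day 183 | 113 + 30 = Day 143 |
| Days after Week 16 | 183 − 113 = 70 | 143 − 113 = 30 |
| Share of window | 70/183 = 38% | 30/143 = 21% |

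**Arm level, by assumed share waived** (share × 70/183 or share × 30/143)

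| Share waived | Dupilumab window unobserved | Upadacitinib window unobserved |
|---|---|---|
| 10% in both arms | 3.8% | 2.1% |
| 25% in both arms | 9.6% | 5.2% |
| 50% in both arms | 19.1% | 10.5% |
| 25% dupilumab, 50% upadacitinib | 9.6% | 10.5% |

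The order reverses once upadacitinib uptake exceeds (70/183)/(30/143) = 1.8 times dupilumab uptake.

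**Effect on a percentage (illustration).** Assume a constant hazard, 30% with an event by Day 113 in both arms, half of each arm waived, and no spontaneous reports. Full-window percentages are 1 − 0.7^(183/113) = 43.9% for dupilumab and 1 − 0.7^(143/113) = 36.3% for upadacitinib. With the waiver they become 0.5 × 43.9 + 0.5 × 30 = 36.9% and 0.5 × 36.3 + 0.5 × 30 = 33.2%.

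**Effect on a rate.** SAP 10.2.1 divides by study drug duration. Under SAP 6.0 that is 99 − 1 + 14 = 112 days for dupilumab and 113 − 1 + 1 = 113 days for upadacitinib. No day after Week 16 enters the denominator; only the numerator can lose events. With equal true event rates, among completers who do not enter Period 2, the apparent upadacitinib/dupilumab rate ratio is:

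- no one waived: (143/113)/(183/112) = 0.77
- 50% waived in each arm: (128/113)/(148/112) = 0.86, where 128 = 143 − 0.5 × 30 and 148 = 183 − 0.5 × 70
- all waived, or a common window to Day 113: (113/113)/(113/112) = 0.99

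So the 30/84-day windows are already unequal with complete collection. An equal-share waiver narrows that gap.

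**Dupilumab subjects who switch in Period 2.** Thirty days after the last upadacitinib dose falls short of Day 183 only if that dose is before Day 153. The shortfall is at most 183 − (113 + 30) = 40 days, for a stop on Day 113. SAP 10.2.1 ends Period 1 the day before Period 2 and then uses 30 days, so collection matches the SAP window and no SAP TEAE days are lost.

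**The case against.** The strongest reply is that the waiver is an openly stated design choice and does not forbid collection. Protocol 6.1 takes spontaneous as well as solicited reports, and its postmarketing route names premature discontinuers only. Serious-event reporting details sit in the Operations Manual, which is not among the documents reviewed. That stands, and it limits the claim: required contact is removed, but it is not shown that events are lost.

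Four stronger readings are tempting, and the documents support none of them.

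- *Events are lost unequally by arm, in a known direction.* The 70 and 30 days are per waived subject. Arm totals need uptake figures that the documents do not give, and the order can reverse.
- *Unobserved time inflates the patient-years.* One might compute, say, 440 × 50% × 70/365.25 = 42 patient-years for dupilumab. That is window time; the SAP denominator is on-drug time and contains none of it.
- *The Period 1 AESI summary is biased.* SAP 10.2.6 ends it at the Week 16 visit, before a completer's waiver takes effect. Only the TEAE-based special-interest lines in SAP 10.2.2 and 10.2.4 could be touched.
- *Switchers fall through the SAP windows by mistake.* SAP 10.2.1 truncates explicitly. What remains is that Protocol 6.1 and 7.5 do not mention the truncation.

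It is also fair to say that keeping the call for everyone would add little to the TEAE tables once the window closes at commercial start. The fix below therefore does not depend on an extra call.

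**Conclusion.** The point holds as a mismatch between collection and analysis windows, together with a conflict between sections. Protocol 5.6, the Synopsis and SAP 2.2 waive follow-up for starters of either drug; Protocol 6.1 does so for the same drug only and is silent on completers' events. Protocol 7.5 and SAP 10.2.1 and 10.3 carry on to 30 or 84 days regardless. Per waived Week 16 completer, up to 70 days on dupilumab or about 30 on upadacitinib count as event-free in TEAE percentages without scheduled observation. Events reported after a change of drug are attributed to the Period 1 drug.

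This rests on nominal visit days, a Week 14 last dupilumab dose and commercial start at the Week 16 visit. For laboratory values the issue is mainly attribution, since Appendix D schedules follow-up laboratory tests only as needed for adverse events. The net effect by arm is unknown, and efficacy is untouched. It should be corrected because the safety comparison otherwise moves with commercial uptake, and because a reader of the TEAE tables cannot tell how much of each window was observed.

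**What to change.** 1. Reconcile the Synopsis, Protocol 5.6 and 6.1, and SAP 2.2 on three points: same drug or either drug; call only or visit and call; and where adverse events of completers who start commercial drug are recorded.
2. Record the date of the first commercial dose.
3. In SAP 10.2.1 and 10.3, end the window at the earlier of 30/84 days after the last dose and the day before the first commercial dose, as SAP 10.2.1 already does at Period 2 start. List later events separately.
4. Report the number of waived subjects by arm.
5. Add a Period 1 TEAE comparison on a common window to the Week 16 visit. Closing the gap at commercial start does not by itself make 30 and 84 days comparable; on the equal-rate calculation the common window brings the ratio from 0.77 to 0.99.
6. For dupilumab subjects who enter Period 2, only align the untruncated wording of Protocol 6.1 and 7.5 with SAP 10.2.1.

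Cost: one date field, one extra table and short text edits.
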